6.0 STUDY PROCEDURES

Overview: There are eight components of the study:

1. Screening and Consent
2. Diagnostic Interview (SCID)
3. Clinical Assessment (psychosis patients only)
4. MRI Scanning
5. Drug Administration
6. Venipuncture
7. Urine pregnancy test (for female participants)
8. Standardized Field-Sobriety Test

[figure not shown]

Figure 1: Study Design

Each component will be described in detail below. The entire study will be completed in three visits over the course of about one week, as demonstrated in **Figure 1**. Visit 1 can be completed virtually. Participants may be contacted by text message the day before the study to remind them of the study visit. The specific rating scales completed will be dependent upon diagnosis and the time since an individual participated in the PGPR study, as many of the measures overlap and assess symptomatology based on specific time-intervals (i.e., the last 2 weeks).

6.1 Screening and Consent: Subjects will be asked if they would like to participate in the current study. This screening will occur over the phone, electronically via zoom, or in person using the Screening Form. Informed consent will be obtained by study personnel directly involved in the research (i.e. research staff or graduate student). Personnel have completed IRB training and have considerable experience running studies on psychiatric populations. Informed consent will be obtained electronically via zoom or in the research offices at the Psychiatric Neuroimaging Program. A research staff member will explain the applicable procedures and the possible risks and benefits to the subjects. The details of the informed consent procedure are as follows:

1. The investigator or research staff and the subject will read together the entire consent form.
2. The subject will be asked details about the study. To document that the subject has read the consent form and has the capacity to understand the most important details, the investigator will use the appropriate Informed Consent Survey. The questions will be read by the investigator or research staff and the answers will be recorded (appropriate response listed in *Italics* in the Informed Consent

Survey). If the subject is unable to answer any of the questions, or if the subject demonstrates a lack of understanding, the investigator or research staff member will then review the details of the study again. Subjects who are unable to answer the questions, even after additional information is provided, will be excluded from the study.

3. The subject will be informed that regardless of whether or not they take part in this research study, it will not affect their treatment, payment or enrollment in any health plans or affect their ability to get benefits or care in any way.
4. The subject will be provided with copies of the signed consent form and the Informed Consent Survey (including the answers given) at the time of the initial visit.

It will be emphasized to all subjects that their participation is completely voluntary, and that even after signing the consent document they are still free to withdraw from the study at any time; in which case they will be compensated for the portion(s) of the protocol they did complete.

6.2 Diagnostic Assessment: Under the supervision of the PI, a trained research assistant will administer the Structured Clinical Interview for DSM-V (SCID) (First, 2015), a clinician-rated assessment of psychiatric disorder. Diagnostic assessments may be conducted electronically with zoom or in the research offices at the Psychiatric Neuroimaging Program. Diagnoses are made both for current and lifetime periods. The SCID is reliable and valid in psychiatric populations, with coefficients of agreement between .70 and 1.0 for depressive, anxiety, and substance use disorders (significantly superior to standard clinical interview). We will supplement the SCID with the psychotic disorders module from the Diagnostic Interview for Genetics Studies (DIGS), which provides more information for the accurate differential diagnosis of psychotic disorders. The Informed Consent Form will include check box indicating if the study participant is being asked to complete the Diagnostic Interview. The SCID can take from 30 minutes to several hours to complete.

If significant suicidal thought is noted during the evaluation, the patients will be encouraged to talk to their treatment providers. If the patient is judged to be at imminent risk of self- or other-harm, standard procedures will be followed (found in Procedures in Response to Suicidal Ideation document).

As stated previously, subjects who were recently recruited in other psychiatry studies also conducted by this PI (PGPR) may not be required to participate in components of this study that would duplicate efforts (e.g. SCID interview). We plan to include data from those studies in the analyses of data from this study. If an excessive time has passed since an individual participated in a PGPR study, portions of the diagnostic interview may be re-administered to determine if there have been any interval changes in a patient's diagnostic status.

6.3 Clinical Assessment (individuals with psychosis only): All clinical tests have been used in our past studies. They are not burdensome and we allow breaks. All scales will be completed before the neuroimaging procedures. All patients are asked to review their substance abuse and current medications at every visit. Clinical assessments may be conducted electronically with zoom or in the research offices at the Psychiatric Neuroimaging Program. The clinical assessments will be completed once in this study (Visit 1).

6.3.a Hamilton Depression Rating Scale (HAM-D): Administrated by a clinician or rater in order to gather data about symptoms independent of the biases inherent in self-report. The version of the HAM-D (Hamilton, 1960) used here incorporates atypical symptoms. It has been used by our group in previous studies, and has been associated with excellent reliability. We will also be using a measure to assess suicidal history and behavior which was developed internally and is composed of questions which would be assessed in any clinical interview. This assessment takes about 15-20 minutes to complete.

6.3.b Positive and Negative Syndrome Scale (PANSS): a 30-item clinician-rated scale designed to rate both presence of active psychotic symptoms and of cognitive symptoms, like alogia, anhedonia,

and flattened affect (Kay et al., 1987). This measure has fair to good psychometrics (Peralta and Cuesta, 1994) and takes about one hour to complete.

6.3.c Personal and Social Performance Scale (PSP): Administered to assess patient's functioning in four main areas: 1) socially useful activities; 2) personal and social relationships; 3) self-care; and 4) disturbing and aggressive behaviors. This measure has high reliability and takes about 5 minutes to complete (Morosini et al., 2000).

6.3.d Young Mania Rating Scale (YMRS): an 11-item clinician-rated measure of manic symptoms. Items are rated on various scales using pre-defined anchors ranging from absent to severe. The measure has adequate psychometrics and takes about 20 minutes to complete (Young et al., 1978).

6.4 MRI Procedures: MRI scans of the brain will be obtained using the MRI scanners in the Center for Human Studies in the Vanderbilt University Institute for Imaging Science (VUIIS), located in the Vanderbilt Hospital and Medical Center North. This will require approximately 60-90 minutes. There will be a total of two MRI scans in this study (Visits 2, and 3). During Visits 2 and 3, the participant will be scanned two hours after receiving the study intervention (LEV or placebo).

6.4.a MRI Screening: The participant will fill out the MRI Procedure Screening Form. The purpose of this form is to ensure that there are no implanted medical devices or metals that could injure the subject if exposed to a high magnetic field. This form will be filled out in a private room adjacent to the MRI scanner and reviewed by the MR Technologist and the research assistant.

6.4.b Scanning Procedures: Imaging studies will take place on a Phillips 3.0 T MRI scanner. The magnet and the magnet's control console are in separate rooms, but the investigator and the subject will be in voice communication at all times, and the investigator will be able to see the subject through a window. All data acquired on the scanner will be securely transferred over the Vanderbilt network to the Institute of Imaging Science's server. Imaging data will be de-identified and only be accessible to the PI, co-investigators, and VUIIS personnel. Scanning procedures may include: 1) Structural imaging, 2) Resting state functional imaging, 3) ASL imaging to non-invasively measure cerebral blood flow, and 4) Functional imaging with task – while in the scanner, participants will view images that include faces, objects and scenes. Images are projected to a mirror above the participants head from a projector located outside the scanner room. Some runs will repeat the same face or object, some runs will present different images. Participants will complete between 1-8 runs of this task. To maximize participant's attention to the images, participants will be instructed to push a button to detect targets. Targets may include image repeats or changes in the image (e.g., image size). This task is similar to the one reported in McHugo et al., 2019.

6.5 Study Drug Administration: During Visit 2, participants will be randomly assigned to an intervention arm in which they will receive two 250mg LEV capsules or two placebo capsules. Both the participant and the research team will be blinded to which arm each participant is in. During Visit 3, the participant will undergo cross-over and receive either two 250mg LEV capsules or two placebo capsules (whichever intervention they did not receive in Visit 2).

6.5.a Dosage Rationale: We selected a 500 mg dosage because of other studies that have been able to safely demonstrate changes in hippocampal activation (Bakker et al., 2015, 2012) using dosages of LEV intervention in patient cohorts outside the FDA-approved indications for LEV. This dosage is well below the typical ranges for efficacy as an antiepileptic with doses of 1,000-3,000 mg/day. Studies using a dosage of 125 mg BID have reported drug levels to be 4.4 mcg/ml +/- 0.53 (mean and SEM), while dosages of 1,000-3,000 mg/day achieve levels of 10-40 mcg/ml (Bakker et al., 2015, 2012; Lyseng-Williamson, 2011). Human results indicating effects with lower dosages are consistent with the

animal literature. Studies that have targeted rats with cognitive impairment and excess hippocampal activity have demonstrated improvements in memory performance using a dosage of 10 mg/kg (Koh et al., 2018, 2010). In another animal model of schizophrenia, dosages of 10 mg/kg improved a sensory gating task performance (Smucny et al., 2015). Typical antiepileptic doses of LEV in rodent seizure models are in a range of 50-150 mg/kg (Ji-Qun et al., 2005; Stratton et al., 2003).

6.5.b. Timing Rationale: We selected a two-hour duration between intervention administration and imaging assessment based on LEV's absorption and clearance data. The pharmacokinetics will be reviewed in more detail in sections 7.2 and 7.3. Briefly, LEV is rapidly and almost completely absorbed after oral administration, with peak serum concentrations occurring approximately one hour after dose (Gambardella et al., 2008). Based on a study that measured LEV plasma concentrations ($\mu\text{mol/L}$) over time after oral ingestion of varying doses of LEV (500-5000mg) in healthy volunteers, LEV levels will be approximately 9.75 mcg/mL (57.3 $\mu\text{mol/L}$) at two hours (Patsalos, 2004). Therefore, two hours after LEV administration is the earliest time-point where we can assess study participants at a sub-therapeutic epilepsy dose (10-40 mcg/mL) of LEV (Bakker et al., 2015, 2012; Lyseng-Williamson, 2011).

6.5.c Concomitant medications: We will allow concomitant use of any medication approved by the US FDA unless specified in our inclusion/exclusion criteria (e.g. normal controls using psychotropic medications). Reviews have indicated that LEV does not affect the metabolism of other drugs, including antipsychotics (Besag and Berry, 2006).

6.5.d Placebo Rationale: We will be using a placebo to improve our ability to test whether LEV is affecting hippocampal activity.

6.6 Venipuncture: Subjects will undergo venipuncture during visits 2 and 3 to assess LEV serum concentration.

6.7. Urine Pregnancy Test: All females will be required to take a urine pregnancy test before intervention administration during Visits 2 and 3, as addressed in the study drug risks below.

6.8 Standardized Field Sobriety Test: Because somnolence is a major side effect of LEV, we require that participants who drive themselves to Vanderbilt Psychiatric Hospital during Visits 2 and 3 (visits with drug administration) will take a Standardized Field Sobriety Test to ensure they are safe to drive themselves home. This test is based on available data provided by the National Highway Traffic Safety Administration. It will be administered before intervention administration and as the final assessment during Visits 2 and 3 immediately before the participant leaves. It takes about 5 minutes to complete. If the participant scores above an impairment threshold on any portion of the test, we will purchase a car service (Uber/Lyft) to drive the participant home and back to Vanderbilt Psychiatric Hospital on another day to obtain their vehicle.

7.0 RISKS - STUDY DRUG

7.1 Risks: Side effects of LEV exposure have been well characterized in clinical trials using LEV dose ranges of 1000-3000 mg/day. The most common symptoms are neurological, including somnolence (15% of patients), asthenia (15%), headache (14%), dizziness (13%), and ataxia (3%) (Ben-Menachem and Falter, 2000; Cereghino et al., 2000; Shorvon et al., 2000). Patients also reported a slightly higher incidence of infection (13% of patients). Up to 13% of patients also experienced adverse neuropsychiatric symptoms. In most of these patients, the symptoms have been mild, including agitation, hostility, apathy, anxiety, emotional lability, and depression (Gambardella et al., 2008). About 1% of patients have experienced serious neuropsychiatric symptoms including hallucinations, suicidal ideations, or psychosis (Kossoff et al., 2001; Mula et al., 2003). In these reports, symptoms occurred mostly within the first month of therapy. Dose reduction or discontinuation

has led to resolution of symptoms in cases reported. Conversely, LEV has no major adverse effects on cognitive function (Neyens et al., 1995), which is an improvement over more traditional anti-epileptic agents (Dooley and Plosker, 2000). Presently, there are no sufficient data to recommend treatment with LEV during pregnancy. Case reports have indicated Stevens-Johnson Syndrome (SJS) is an exceedingly rare side effect of LEV administration (Zou et al., 2012). In a meta-analysis of 26 double-blind, randomized, placebo-controlled trials (2832 patients), no dose-response relationship was found for any side effects (Verrotti et al., 2015).

7.2 Absorption and Distribution: LEV is rapidly and almost completely (>95%) absorbed (Rossetti and Bromfield, 2005) after oral administration of doses ranging from 250 to 5000 mg, with peak serum concentrations occurring approximately 1 hour after dose and steady state concentrations are reached within 48 hours (Gambardella et al., 2008). The oral bioavailability of LEV capsules is 100%. Food does not affect the absorption of LEV. The volume of distribution is 0.5-0.7 L/kg (Patsalos, 2004). LEV does not bind to plasma proteins and has linear pharmacokinetics that are time-invariant with low intra- and inter-subject variability (Patsalos, 2004, 2000).

7.3 Metabolism and Elimination: LEV is not extensively metabolized in humans. The major metabolic pathway is the enzymatic hydrolysis of the acetamide group by a plasma hydroxylase. This produces the inactive compound carboxylic acid metabolite ucb L057 (24% of dose). LEV does not undergo hepatic metabolism (Nicolas et al., 1999). The serum half-life is 6 to 8 hours (Krasowski, 2010). LEV is eliminated from systemic circulation by renal excretion as unchanged drug (66% of the dose). Total body clearance is 0.96 mL/min/kg and renal clearance is 0.6 mL/min/kg. The metabolite ucb L057 is renally excreted with a renal clearance of 4 mL/min/kg. Clearance is rapid, so that within 48 hours approximately 93% of an oral dose is eliminated. In patients with renal impairment, doses should be reduced in accordance with creatinine clearance (Patsalos, 2004).

7.4 Interactions with other Drugs: Reviews have indicated that LEV does not affect the metabolism of other drugs, including antipsychotics (Besag and Berry, 2006).

7.5 Minimizing Risk for Study Drug:

7.5.a Dosage: As mentioned above, clinical indications for LEV use in epilepsy range from 1000-3000 mg/day. Our study will be using 500 mg. As reviewed in both section **3.0** and **6.5.b**, human functional MRI studies have demonstrated that low doses decrease hippocampal activity and improve memory task performance in patient cohorts outside the FDA-approved indications for LEV.

7.5.b Screening Process: Visit 1 will include a Screening Form that has a LEV Screening section. It will assess neuropsychological history to address the neuropsychological side effects and assess history of rashes in response to medications to address the possibility of a SJS reaction. Females will perform a pregnancy test before drug administration to ensure no teratogenic effects.

7.5.c Usage as add-on therapy for psychosis cohort: LEV has no known major drug interactions. Therefore, the psychosis cohort will use LEV as an add-on therapy with the antipsychotic medications.

7.5.d Driving after drug administration: Because somnolence is a major side effect of LEV, we require that participants who drive themselves to Vanderbilt Psychiatric Hospital during Visits 2 and 3 (first day of drug administration) will take a Standardized Field Sobriety Test to ensure they are safe to drive themselves home. This test is based on available data provided by the National Highway Traffic Safety Administration. It will be administered before intervention administration and as the final assessment during Visits 2 and 3 immediately before the participant leaves. It takes about 5 minutes to complete. If the participant scores above an impairment threshold on any portion of the test, we will purchase a car service (Uber/Lyft) to drive the participant home and back to Vanderbilt Psychiatric

Hospital on another day to obtain their vehicle.

7.6 Risk/Benefit Ratio: When the safety record outlined above is considered, the risks of participation in this study are low. Safety of LEV appears to be very favorable. Subjects participating in these studies will receive MRI assessment and basic drug and pregnancy screening (when applicable) at no cost to them. Otherwise, there are no direct benefits to the subjects participating in this research. The long-term potential benefit of this study is a mechanistically directed approach toward identifying a reliable biomarker for psychotic disorders. Every research study requires the potential benefits to outweigh the potential risks of the study. The potential benefit of establishing a biomarker is significant for public health, including for patients, their families, communities, and healthcare systems. While the study procedure confers greater than minimal risk, the low likelihood of serious adverse effects is outweighed by the potential public health benefits stemming from the potential results of this study and subsequent studies based on these results.

With respect to MRI scanning, the MR system requires the use of rapidly varying magnetic gradient fields and strong radio frequency fields. These switched gradient and radio frequency fields conform to the guidelines established by the US FDA for time varying magnetic fields in MR devices. No serious or lasting incidents or side effects associated with the use of high field magnets have been reported. Based on this experience, and valid scientific evidence, the FDA has found that this does not pose a significant risk to human subjects.

8.0 RISKS – OTHER THAN THE STUDY DRUG

8.1 Psychological and Behavioral Assessment Risks: At screening, subjects will undergo non-invasive psychological assessment of a structured nature that has been consistently used without adverse effects in previous studies with a similar subject population. There is the potential risk that subjects may become fatigued during the performance of screening assessments or behavioral tasks, and that discussion of personal issues with study personnel in the context of screening issues may be stressful or uncomfortable. Because subjects participating in this study will be stable outpatients, it is unlikely that the stress posed by such measures will exacerbate baseline psychiatric symptoms.

Minimizing the Risk of Psychological and Behavioral Assessment: The risk of the diagnostic evaluation involves the possibility that participants may be asked questions which cause them distress. These would be questions consistent with any clinical evaluation. In order to address this risk, participants will be told they can decline to answer any questions and can stop the evaluation at any time.

8.2 MRI Scan Risk:

1. Ferromagnetic objects brought into the room will be pulled toward the magnet.
2. Due to the magnetic properties of the scanner, if a subject has implanted metal or medical devices they may experience abnormal torques or failure to function properly. This may cause injury to the body areas where the device is located.
3. There is a risk of tissue heating if there is excessive power deposition of radiofrequency (RF) magnetic waves. Excessive RF waves emitted could cause the atoms to transmit high-frequency RF wave at such a rate as to cause the neighboring tissue to heat.
4. There is a risk of peripheral nerve stimulation if gradients are switched too rapidly. Switching a gradient will increase the magnetic field strength in specific area. This in turn, increases the current in that area. If the field strength is switched too rapidly, the amount of current will increase to the point of tissue excitation.
5. The subjects may experience a claustrophobic reaction in the magnet.
6. There are loud banging noises with MR imaging that may be uncomfortable.

Regarding the MRI procedures we will employ the following protections:

1. The subject will be instructed not to bring metal objects into the magnet room and will be provided with lockable facilities for personal belongings.
2. The use of the MRI screening form will exclude from the study potential subjects with implanted metal or

medical devices.

3. The FDA has strict limits regarding power deposition. Safeguards built into the operating system prevent exceeding those limits.
4. The FDA has strict limits regarding gradients strengths and rise times. Safeguards built into the operating system prevent exceeding those limits.
5. Subjects will be warned of the potential for claustrophobic reactions and those with a prior history of such reactions will be excluded from the study. If a subject experiences an unexpected and severe claustrophobic reaction, the study will be terminated.
6. Subjects will be provided with hearing protection.

Potential Risks to Subjects (Rare/Unforeseen): There have been no appropriate studies that either rule out or demonstrate negative health effects of MRI on fetuses. We will inform women with child-bearing potential of this information and pregnant women will not be allowed to participate. If new information becomes available to suggest that MRI may not be safe for pregnant women or their fetuses we will inform the subjects of such information.

8.3 Venipuncture risk: Commonly, there may be discomfort or pain at the site at the time of venipuncture, or bleeding or bruising post-venipuncture. Uncommonly, there is a very small risk of infection, which can be treated. Participants will be asked to contact their PCP and the study PI in the event of any adverse outcome.

8.4 Minimizing risk of Breach of Data Security and Privacy: Data obtained from human subjects will be confidential and accessed only by members of the study team with appropriate IRB and HIPAA training, as assured by standard training protocols at VUMC. Data is maintained and secured in locked file cabinets or on encrypted, password protected computers, located in locked offices, and following Health Insurance Portability and Accountability Act (HIPAA) guidelines and the policies and procedures of VU and VUMC. Individuals will be identified by a numerical code that will be kept separate from study data.

9.0 REPORTING OF ADVERSE EVENTS OR UNANTICIPATED PROBLEMS INVOLVING RISK TO PARTICIPANTS OR OTHERS

We define an adverse event as any adverse change in health or development of a side effect occurring in a study participant after enrollment. These may be expected events (known drug effects, as detailed in the consent form, safety monitoring plan, or package insert) or unexpected events. The PI and Co-investigators will review any AE's that occurred during a participant's study experience, and determine their magnitude and causal attribution using the scale below. Every six months the PI and Co-investigators will review the magnitude and frequency of AE's and report such information to the IRB. All AE's will be documented in REDCap using an Adverse Event Form.

AE's of grade three or higher in the scale below will be reported immediately to the IRB using the Report of Adverse Events form and to the Program Director of the appropriate funding agency. In conjunction with the IRB, the PI then will determine if modifications to the protocol are warranted.

The primary method for ensuring data accuracy and protocol compliance will be the involvement of the PI in all aspects of the project. The PI and IRB have the authority to stop or modify the study at any time. During the semi-annual reviews, the PI and IRB will together decide if the study should continue unchanged, be modified, or closed to further enrollment.

An independent safety monitor (ISM) will also review this study for safety and adherence to the study protocol. The ISM will meet with the study PI every 6 months to assure safety of research participants, regulatory compliance, and data integrity. The ISM is distinctly separate from the role of the PI. A report will be generated after every ISM meeting and communicated with the IRB if needed.

Scaling of Adverse Events: Attribution of Cause:

- a. Definite: Adverse event (AE) will clearly be related to investigational agents or other intervention.
- b. Probable: AE will likely be related to investigational agents or other intervention.
- c. Possible: AE may be related to investigational agents or other intervention.
- d. Not Likely: AE will doubtfully be related to investigational agents or other intervention.
- e. Unrelated: AE will clearly not be related to investigational agents or other intervention.

Grading of Severity

0: No AE or within normal limits.

1: Mild AE.

2: Moderate AE.

3: Severe AE resulting in inpatient hospitalization, a persistent or significant disability/incapacity, or a congenital anomaly/birth defect.

4: Life-threatening or disabling AE.

5: Fatal AE

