5.0 ENROLLMENT

5.1. Recruitment: Study participants will be recruited from the **Psychiatric Genotype/Phenotype Repository (PGPR, IRB #080606)**: The PGPR study includes a clinical interview during which diagnostic and clinical history data is collected. At the end of this interview, individuals will be asked by one of the key research personnel listed on this application if they are interested in participating in the study. The PI of this study is the same PI for the PGPR study. Subjects will be read a script describing the study. Subjects will be told that the study is separate from their participation in the PGPR study and choosing not to participate in the study will not affect their participation in the PGPR study. In addition, individuals that have previously completed the PGPR study may be contacted and asked if they would like to participate in the study. The consent form for the PGPR study states that subjects may be contacted and asked if they would like to take part in future studies, if they agree. Subjects will be read a script telling them about the study. The telephone screening form used for the Psychiatric Genotype/Phenotype study will be re-administered to make sure that they still meet the original criteria for participating in the Psychiatric Genotype/Phenotype Study (i.e. age, physical health, and MRI requirements).

We will make every effort to recruit equal numbers of men and women. We will not exclude subjects based on gender or minority status. We minimize coercion throughout the study by repeatedly informing subjects that

they may discontinue study procedures at any point, or opt-out of any specific part of the study they become uncomfortable with completing.

We plan to recruit up to 80 subjects (up to 40 healthy control subjects and up to 40 patients with psychotic disorders) for the study. We hope to acquire analyzable data from at least 20 control subjects and 20 patients.

Subjects who were recently recruited in other psychiatry studies also conducted by this PI (e.g. genotype/phenotype studies) may not be required to participate in components of this study that would duplicate efforts (e.g. SCID interview). We plan to include data from those studies in the analyses of data from this study. Participants will be compensated for all activities they complete.

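### Grade 3 mixes intensity with outcome, so some severe adverse events fit no grade, a mild or moderate event leading to admission stays at grade 1 or 2, and both miss immediate reporting

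*Combined protocol and SAP*

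**What the plan says.** All of this is in Section 9.0 of the combined protocol and SAP unless stated otherwise.

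The severity scale runs from 0 to 5. Grades 1 and 2 are the single words mild and moderate, with no outcome attached. Grade 3 is "3: Severe AE resulting in inpatient hospitalization, a persistent or significant disability/incapacity, or a congenital anomaly/birth defect". Grade 4 is "4: Life-threatening or disabling AE", and grade 5 is a fatal event.

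The scale drives one reporting rule: "AE's of grade three or higher in the scale below will be reported immediately to the IRB". The same rule sends the report to the funding agency's programme director, and the PI then decides with the IRB whether the protocol needs changing.

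Events below grade 3 follow the routine path: "All AE's will be documented in REDCap using an Adverse Event Form", and "Every six months the PI and Co-investigators will review the magnitude and frequency of AE's and report such information to the IRB". An independent safety monitor works to the same interval: "The ISM will meet with the study PI every 6 months to assure safety of research participants".

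**The concern.** Intensity (how bad the event is) and seriousness (what it led to) are separate attributes. Grades 1 and 2 use intensity alone, grades 4 and 5 use outcome, and grade 3 requires both together. A scale built this way can leave combinations uncovered, and here the uncovered ones lie at the boundary that decides whether the IRB and funder hear at once.

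Such events are plausible. Section 8.2 foresees a severe claustrophobic reaction in the scanner that would end participation. If nobody is admitted or disabled, that event is severe but has no grade 3 outcome. Section 7.1 names reactions such as hallucinations, suicidal ideation and psychosis, and says the reported cases resolved when the drug was reduced or stopped. A reversible reaction is less likely to meet a criterion of lasting disability. Up to 40 of the participants have a psychotic disorder, and every participant who completes the crossover receives the drug.

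What is at stake is timing. A participant's visits take about one week (Section 6.0), while the routine review comes every six months, roughly 26 weeks. An event that misses the trigger could wait until that participant and many later ones have finished, which also delays the decision on modifying the protocol.

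**Working it through.** The plan states no figure on this point, so there is none to reproduce. The check applies the grade definitions literally to each combination of intensity and outcome.

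**Inputs (Section 9.0).** Grade 1 = mild. Grade 2 = moderate. Grade 3 = severe AND (admission OR persistent or significant disability/incapacity OR birth defect). Grade 4 = life-threatening OR disabling. Grade 5 = fatal. Immediate reporting if grade ≥ 3. Assumption: where two grades fit, the higher is used.

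| Outcome | Mild | Moderate | Severe |
|---|---|---|---|
| None of those listed | 1, routine | 2, routine | **no grade, routine** |
| Inpatient admission | **1, routine** | **2, routine** | 3, immediate |
| Birth defect | **1, routine** | **2, routine** | 3, immediate |
| Disability or incapacity | 1, or 4 if judged disabling | 2, or 4 if judged disabling | 3 or 4, immediate |
| Life-threatening | 4, immediate | 4, immediate | 4, immediate |
| Fatal | 5, immediate | 5, immediate | 5, immediate |

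**Result 1.** Exactly one cell has no grade: severe, with no listed outcome, and not life-threatening, disabling or fatal. With no grade, it cannot satisfy a rule that starts at grade 3.

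**Result 2.** Admission without severe intensity is grade 1 or 2 on the literal text, so it also misses the rule. The birth-defect cells behave the same way.

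**Result 3.** Disability appears in grade 3 and, as disabling, in grade 4. For a severe event both grades trigger immediate reporting, so the overlap does not change what is reported.

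**Other routes.** Section 9.0's heading mentions unanticipated problems, but its text gives them no separate trigger. Section 6.2 refers to a suicidality procedure, but describes it as a response to risk noted at the diagnostic evaluation and states no IRB route. The safety monitor's stated interval is six months. No supplied text gives the uncovered cells an immediate route.

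**Can the frequency be derived?** The only related rate is the 1% in Section 7.1. If q is the unknown share of such events that falls in the gap, the chance of at least one among n people dosed is 1 − (1 − 0.01q)^n.

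- q = 0: the chance is 0 for any n.
- q = 1, n = 40: 1 − 0.99^40 = 0.331.
- q = 1, n = 80: 1 − 0.99^80 = 0.552.

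The documents give no value for q, so the result runs from 0 to 33% (40 patients) or from 0 to 55% (all 80), even if the 1% is accepted. The range is too wide to size the gap, and it leaves out events that are not neuropsychiatric.

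**The case against.** The strongest reply is that little is lost. Every event is recorded whatever its grade. The PI and co-investigators judge the magnitude and cause of each one, the IRB sees them in the six-monthly report, an independent monitor reviews safety, and the PI and IRB may stop or modify the study at any time. Section 9.0 also mentions a safety monitoring plan and Section 6.2 a suicidality procedures document. Neither was supplied, so a further escalation route cannot be excluded. All of this stands, and it limits the point to immediacy and grading. It does not repair the rule, because discretion to act at any time is not a duty to report at once.

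Several stronger readings are tempting, and the documents do not support them.

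- A reader might infer that any severe psychiatric reaction managed without admission escapes. It does not: one judged life-threatening or disabling is grade 4 and is reported immediately. Acute suicidal ideation may well be judged so, and marked hallucinations might be read as significant incapacity. Whether a given case falls in the gap depends on that judgement.
- A reader might infer that the ungraded event is recorded as grade 2. Staff may choose that as the nearest entry, but grade 2 is labelled moderate and nothing assigns a severe event to it.
- A reader might take "About 1% of patients have experienced serious neuropsychiatric symptoms including hallucinations, suicidal ideations, or psychosis" as the rate for this gap and expect a 33% to 55% chance of a missed event. That rate covers all such symptoms, including those already in grades 3 to 5. It sits among safety data on 1000-3000 mg/day, with onset mostly in the first month of therapy, whereas here the drug is given at one visit at 500 mg. At an assumed 0.1% to 0.5%, the same formula with q = 1 gives 4% to 18% in 40 and 8% to 33% in 80, still before removing events that are already covered.
- A reader might infer that the trial's results are distorted. Section 11.2 plans no adverse-event analysis, so no planned estimate uses the grade distribution.

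**Conclusion.** The point holds in a limited form. Read literally, the scale leaves one class of severe event without a grade and leaves non-severe events that lead to admission at grade 1 or 2. Followed as written, the grade 3 rule sends both to the six-monthly report. This is a wrong rule, not merely missing detail: the definitions are complete enough to apply, and applying them gives the wrong route.

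The consequence is delayed notice to the IRB and funder and an absent or misleading grade. The event itself is not lost, and the trial's estimates do not change. The number of events affected cannot be derived from the documents.

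The conclusion assumes that the grade definitions are applied as worded and that no document outside the supplied text provides another immediate route. It should be corrected because the amendment is small and the safety rule then does what it appears intended to do.

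**What to change.** Separate the two ideas in Section 9.0 and carry the change into the REDCap adverse event form:

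1. Define grade 3 as any severe adverse event, with no outcome condition.
2. Add a second trigger for immediate reporting, independent of intensity: any event that results in admission, lasting or substantial disability or incapacity, or a birth defect is reported at once, whatever its grade.

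Both parts are needed. Loosening grade 3 alone would still miss a moderate event that leads to admission.

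Optionally, place disability in only one of grades 3 and 4. This tidies the scale but changes no reporting.

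The cost is a wording amendment, a revised form and some additional immediate reports, including severe but self-limiting events such as severe headache or somnolence. Their number cannot be estimated, because Section 7.1 gives overall rates for those side effects without a breakdown by severity.
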